# **GLOSSARY OF ABBREVIATIONS**

T1DM	Type 1 Diabetes Mellitus
T2DM	Type 1 Diabetes Mellitus Type 2 Diabetes Mellitus
DM	Diabetes Mellitus

# **KEYWORDS**

Diabetes Mellitus, Pregnancy, Women, Knowledge

# STUDY SUMMARY

TITLE Contraception and pregnancy in diabetes mellitus

**DESIGN** Non-interventional, Cross-sectional study

AIMS To examine the knowledge base women of reproductive age with diabetes

have regarding contraception and pregnancy

**OUTCOME MEASURES** Quantitative and qualitative questionnaires

**POPULATION** n=100

**ELIGIBILITY** Women of reproductive age (18-52) with diabetes

**DURATION** 1 hour per participant, 5 months total

# 1. INTRODUCTION

# 1.1 Background

Worldwide, 44% of pregnancies are unplanned (Bearak et al. 2018); in the UK 45% of pregnancies and one third of births are unplanned (Public Health England). If a woman wants 2 children, she will spend, on average, 5 years trying to conceive or being pregnant, and 30 years trying to prevent pregnancy (Gnoth *et al.* 2003; Jensen *et al.* 2001).

Women with diabetes are known to have 'high-risk' pregnancies. Complications for the mother include worsening diabetic control, particularly with increased hypoglycaemia in the 1st trimester; deterioration in retinopathy and nephropathy; pre-eclampsia; birth trauma due to fetal macrosomia (Weissgerber & Mudd 2015; Temple et al 2001; Alexopoulos et al 2019). For the fetus, there are increased risks of congenital abnormalities; macrosomia with resultant birth trauma including shoulder dystocia; intrauterine growth restriction; miscarriage; still birth; neonatal unit admission and neonatal death (Ludvigsson et al, 2018; Jensen et al 2009; Jensen et al 2004).

NICE guidance (NG3) contains a number of recommendations to prepare women with diabetes for a healthy pregnancy, and recommendations to avoid a pregnancy in poorly controlled diabetes; it also has recommendations about contraception. However, the National Diabetes in Pregnancy Audit 2019 shows that seven out of eight women are not adequately prepared pre-pregnancy, and there are still increased numbers of neonatal deaths, stillbirths, congenital anomalies, large and small for gestational age babies and neonatal unit admissions, compared to pregnancies in women without diabetes. The cause for these poor outcomes, despite the NICE guidance, needs to be understood to enable pregnancy outcomes to improve. One likely factor is poor patient knowledge about the complications associated with pregnancy. One study, undertaken in 2009, showed that only 35% of women with diabetes of reproductive age recalled having any discussion about pregnancy, and only 25% were aware of any of the risks associated with pregnancy (Cartwright et al; 2009). Another study in women with diabetes seen in an antenatal clinic showed that even if a woman was aware of the risks associated with diabetes in pregnancy, she often did not attend for pre-conception counselling and preparation (Murphy et al; 2010). The reasons for this were multifactorial, including falling pregnant faster than expected, and pervious poor interactions with healthcare professionals.

# 1.2 Rationale for current study

This study seeks to expand upon and update this body of work. It will explore the knowledge and understanding women with diabetes have around pregnancy and conception, as well as establish how well prepared these women are for a pregnancy. Using this data, we will develop better services to inform women with diabetes about the contraception and pregnancy, as well inform the development of pre-conception counselling services for women with diabetes. If successful, we would anticipate seeing an improvement in performance in future National Diabetes in Pregnancy audits.

# 2. STUDY OBJECTIVES

# **Primary Objective**

- To establish what knowledge women of childbearing age with diabetes have of
  - o The risks and management of diabetes in pregnancy
  - o The effect of diabetes on fertility
  - o What forms of contraception women with diabetes use

# **Secondary Objective**

- To describe the typical diabetes treatment regimes in women with diabetes of reproductive age.
- To determine the overall diabetes control in women with diabetes of reproductive age.
- To examine the number of women of reproductive age who have diabetes-related complications.

# 3. STUDY DESIGN

Non-interventional, cross-sectional questionnaire study in women of child-bearing age 1 hours per participant, 6 months total n=100 participants total

# 3.1 Study Outcome Measures

- Quantitative data:
- Number of women planning a pregnancy within the next year
- Invitation to and attendance at pre-conception counselling
- Current contraceptive choices
- Knowledge of effect of diabetes on fertility
- Number of women who have had the importance of a planned pregnancy explained to them
- 2. Descriptive data
- Women's knowledge of the risks to the mother during pregnancy if the mother has diabetes
- Women's knowledge of the risks to the fetus during pregnancy if the mother has diabetes

Additional baseline participant data:

- Age
- Ethnicity
- · Number of previous pregnancies
- Type of diabetes
- · Length of diabetes
- Current diabetes treatment
- Diabetes complications: nephropathy, neuropathy, retinopathy, cardiovascular disease
- Recent HbA1C
- Other medical conditions
- Other medications

# 4. PARTICIPANT ENTRY

### 4.1 Pre-registration evaluations

Potential participants will be identified by the clinical diabetes team from the list of people who attend the diabetes clinics at Imperial College Healthcare NHS Trust.

#### 4.2 Inclusion Criteria

- Women aged 18-52 years (reproductive age) who are not currently pregnant
- Previous diagnosis of Diabetes Mellitus

# 4.2 Exclusion Criteria

- Inability to understand and write in the English language
- Unable to participate due to other factors, as assessed by the Chief Investigators
- A history of gestational diabetes but not diabetes mellitus.
- Pregnant women

#### 4.3 Withdrawal criteria

- Loss of capacity to give informed consent
- Investigator initiated discontinuation of study due to participation concerns

Withdrawal will be immediate, and participants will be followed up in the appropriate outpatient diabetes clinic at their usual appointments.

If a participant, who has given informed consent, loses capacity to consent during the study the participant will be withdrawn from the study. Identifiable data already collected with consent will be retained and used in the study. No further data would be collected or any other research procedures carried out on or in relation to the participant.

### 5. ADVERSE EVENTS

#### 5.1 Definitions

Adverse Event (AE): any untoward medical occurrence in a patient or clinical study subject.

**Serious Adverse Event (SAE):** any untoward and unexpected medical occurrence or effect that:

- Results in death
- Is life-threatening refers to an event in which the subject was at risk of death at the time of the event; it does not refer to an event which hypothetically might have caused death if it were more severe
- Requires hospitalisation, or prolongation of existing inpatients' hospitalisation
- Results in persistent or significant disability or incapacity
- Is a congenital anomaly or birth defect

Medical judgement should be exercised in deciding whether an AE is serious in other situations. Important AEs that are not immediately life-threatening or do not result in death or hospitalisation but may jeopardise the subject or may require intervention to prevent one of the other outcomes listed in the definition above, should also be considered serious.

# 5.2 Reporting Procedures

All adverse events should be reported. Depending on the nature of the event the reporting procedures below should be followed. Any questions concerning adverse event reporting should be directed to the Chief Investigator in the first instance.

#### 5.2.1 Non serious AEs

All such events, whether expected or not, should be recorded.

#### 5.2.2 Serious AEs

An SAE form should be completed and faxed to the Chief Investigator within 24 hours. However, relapse and death due to diabetes mellitus, and hospitalisations for elective treatment of a pre-existing condition do not need reporting as SAEs.

All SAEs should be reported to the <a href="c

- 'related', i.e. resulted from the administration of any of the research procedures;
   and
- 'unexpected', i.e. an event that is not listed in the protocol as an expected occurrence

Reports of related and unexpected SAEs should be submitted within 15 days of the Chief Investigator becoming aware of the event, using the NRES SAE form for non-IMP studies. The Chief Investigator must also notify the Sponsor of all SAEs.

Local investigators should report any SAEs as required by their Local Research Ethics Committee, Sponsor and/or Research & Development Office.

Contact details for reporting SAEs [contact]

CI email (and contact details below)

[contact] for attention [name] Please send SAE forms to: Department of Diabetes and Endocrinology, St Mary's

Hospital, [name] [contact] (Mon to Fri 09.00 – 17.00)

# 6. ASSESSMENT AND FOLLOW-UP

This study will consist of completing a questionnaire. This should take no more than 1 hour to complete by the participant at a time and location convenient to them.

All eligible participants will be identified by the clinical care team. A list of potential participants will be identified from the database of all people who attend the diabetes clinics at Imperial College Healthcare NHS Trust (subsequently known as the participant database).

Potential participants will be contacted in one of 3 ways by the clinical team:

- a) Participants whose emails are available on Cerner will be contacted by email by a member of their direct care team (who is also part of the research team). The email will include the PIS and a link to Qualtrics (an online data collection platform which is supported by the college). Informed consent will be taken via this platform with questionnaires to follow (only accessible if participant has consented to all clauses and signed electronically). Participants will be able to arrange a phone call with the research team to discuss any issues or concerns before signing the consent if they wish. Participants will be provided with a unique code to enable researchers to link their questionnaire data with their medical records. This will be different to the study code and which will be assigned to participants after consent in order of enrolment.
- b) For potential participants whose emails are not available or who prefer a hard copy approach, study packs, including the patient information sheet, consent form and questionnaire will be sent by post for completion at home, and returned in a pre-paid addressed envelope to the research team.
- c) Patients who are seen in clinic by either the diabetes team will be approached by their clinical team about participating in the study. Those who are interested will then be provided with a consent form and study questionnaire which can either be completed and returned to the research team whilst in the clinic or taken home and returned in a stamped addressed envelope at the participant's convenience.

In all cases, the research team will make blank study packs (including the consent form, patient information sheet and questionnaire) which can be addressed to the individual woman by the clinical team. All women will be asked to return the questionnaire by the end of the study for inclusion in the study analysis.

Within the patient information sheet there will be contact details for the research team, should the participant wish to discuss the study and obtain any further details.

Once returned, the pseudonymised questionnaire data will be recorded in a password encrypted database on an Imperial College Healthcare NHS Trust computer (subsequently known as the results database). Informed consent will be filed in the trial master file. Data from Qualtrics will be downloaded in a PDF format on either an ICL or ICHT computer and printed for hard copy records. Questionnaire scoring data will be pulled from Qualtrics in a

pseudonymised format and saved on either an ICL or ICHT computer within an encrypted, password protected document.

Once informed consent has been provided, The research team will then review the electronic health records of those participants who have consented to record biochemical data, medical history and baseline demographics. This data will be recorded in pseudonymised form in the results database.

In all cases, no samples are taken and all data will be pseudonymised. No follow up outside of usual care will be provided.

End of study will be defined as last subject last visit (LSLV).

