# 7. STATISTICS AND DATA ANALYSIS

Approximately 100 potential participants will be identified from the list of persons who attend the Imperial College Healthcare NHS Trust diabetes clinics. This is based on the known total number of people who attend these clinics (approximately 2000), assuming that 50% will be women and 50% of these will be of reproductive age. All potential participants will be sent the study pack. A response rate of 10-20% is assumed following previous questionnaire studies undertaken at Imperial College of patient populations.

This study contains both descriptive and quantifiable data. The quantitative outcomes may be either ordinal or categorical, and proportions tests, including Chi squared tests, t-tests and ANOVAs will be used to determine differences between these outcomes.

The descriptive data will be tabulated and presented as such without statistical analysis.

All personal details will be sent via encrypted email (nhs.net).

Record linking participant information to study ID will be stored securely on an Imperial College NHS trust Computer. All study data will be stored in a pseudonymised format in an encrypted database on an Imperial College NHS trust computer.

Direct quotations may be published in anonymous fashion. Care will be taken to ensure no other incidental details (such as ethnicity or age) will be associated with the quotation, in order to ensure anonymity. The NHS Code of Confidentiality will be followed at all times. All data is to be stored in a pseudonymised form by using study codes for de-identification of participants. Examples of such a code includes: CAPRE-DM 0001 (assigned in order of enrolment). Identifiable Personal data will be kept in files in a locked office within Imperial College Healthcare NHS Trust, accessible only by the research/clinical team. Pseudonymised data will be stored in a password encrypted spreadsheet on ICHT computers, accessible only by the research team.

Data and all appropriate documentation will be pseudonymised and stored for a minimum of 10 years after the completion of the study in line with Imperial College policy.

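### Courtesy answering may raise the self-reported counselling and explanation outcomes, because the plan does not separate a woman's answers from her own clinicians

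*Combined protocol and SAP*

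**What the plan says.** **Who makes contact.** Section 6 states: "Potential participants will be contacted in one of 3 ways by the clinical team". On route (a), email, the women are "contacted by email by a member of their direct care team (who is also part of the research team". Route (b) is a postal pack. On route (c) the clinical team approaches women attending clinic.

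**How answers come back.** The questionnaire is self-completed, "by the participant at a time and location convenient to them". Postal forms go to the research team. Route (c) forms may be "completed and returned to the research team whilst in the clinic or taken home and returned in a stamped addressed envelope".

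**Whether answers can be tied to a woman.** On route (a) each participant receives a "unique code to enable researchers to link their questionnaire data with their medical records". On routes (b) and (c) the consent form and questionnaire are issued together.

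**Who has access.** Section 7 makes identifiable personal data "accessible only by the research/clinical team". The sentence that follows restricts the pseudonymised data to the research team.

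**What is asked.** The quantitative outcomes in section 3.1 include invitation to and attendance at counselling, and "Number of women who have had the importance of a planned pregnancy explained to them". Current contraception and plans for pregnancy within a year are also listed.

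**What is not there.** The record review in section 6 covers biochemistry, medical history and demographics. It does not mention counselling or invitations. Section 7 plans no analysis by route, and no section deals with socially desirable answering.

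**The concern.** The two counselling items ask a patient, in effect, whether the service that looks after her gave the advice it should have given. A woman who was not counselled may answer *yes* because she thinks the people who treat her will read the reply. This differs from poor recall: the pressure comes from who is seen to receive the answer.

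Several features of the plan combine to create that pressure. The approach comes from the clinical team, at least one direct-care member is also a researcher, a form can be handed over in the clinic, and answers are linkable to records. Coding does not remove the pressure, because it is applied to answers that the team can already link to a named woman.

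Section 1.2 says the study is meant to guide better services and to update earlier work. Falsely positive answers would hide the gaps that the survey is looking for, and could look like progress since the 2009 study cited in section 1.1. The error would not shrink with more respondents, and it cannot be removed once the answers are in.

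**Working it through.** **1. The plan's own number.** Section 7 gives about 2000 attenders, 50% women, 50% of those of reproductive age, and a 10–20% response. 2000 × 0.5 × 0.5 = 500 women; 500 × 0.10 = 50 and 500 × 0.20 = 100 respondents. The planned n=100 is reached at the upper response rate. (Section 7 also describes about 100 as the number of *potential* participants, which its inputs do not give. That is a separate matter.) The plan states no precision target.

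**2. Model for a self-reported *yes*.** Let p be the true share counselled, f the share of women not counselled who say they were (courtesy), and g the share counselled who do not recall it (forgetting).

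Observed = p(1 − g) + (1 − p)f

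The documents give neither f nor g, so both are assumed. For p, 35% is used for illustration only. It is the share in the 2009 study (section 1.1) who recalled any discussion of pregnancy. That is itself a recalled answer, and to a different question.

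**3. Results at p = 35%** (net error in points in brackets)

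| f | g = 0 | g = 10% | g = 20% |
|---|---|---|---|
| 5% | 0.35 + 0.65×0.05 = 38.3% (+3.3) | 34.8% (−0.3) | 31.3% (−3.8) |
| 10% | 0.35 + 0.65×0.10 = 41.5% (+6.5) | 38.0% (+3.0) | 34.5% (−0.5) |
| 20% | 0.35 + 0.65×0.20 = 48.0% (+13.0) | 44.5% (+9.5) | 41.0% (+6.0) |

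Forgetting cancels courtesy exactly when g = (1 − p)f / p, which is 9.3%, 18.6% and 37.1% for f = 5%, 10% and 20%.

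**4. Other true rates.** Courtesy alone adds (1 − p)f. At p = 25% that is 3.8, 7.5 or 15 points; at p = 50% it is 2.5, 5 or 10 points.

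**5. Yardstick.** The 95% half-width is 1.96 × √(p(1 − p)/n). At p = 35%, n = 100: 1.96 × √(0.35 × 0.65/100) = 9.3 points. At n = 50 it is 13.2 points. At n = 100 it is 8.5 points for p = 25% and 9.8 points for p = 50%.

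Courtesy at 5% or 10% therefore stays inside sampling error at n = 100, and 20% exceeds it unless forgetting offsets it.

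**6. Access wording.** The clause naming the combined research and clinical team covers identifiable personal data, and the results database is for the research team only. Section 6 nevertheless places a direct-care member in the research team. The restriction therefore does not by itself keep a woman's answers from someone who treats her.

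**The case against.** The strongest case against is that most of the mechanism is inferred. Completion is private on routes (a) and (b), every return is addressed to the research team, and the pseudonymised results are closed to the wider clinical team. The dual role is stated only for route (a). The questionnaire and information sheet are not available here, so women may already be told who sees their replies. Section 3.1 does not say who was to have given the explanation, so reading that item as a rating of this clinic is an inference. The counselling and explanation items are in the outcome list but are not named in the primary objective.

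These points stand, and they limit the claim. They do not remove it: no passage prevents a woman's own clinician, acting as a researcher, from opening her form.

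Three stronger readings are tempting and are not supported:

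- *The counselling results will be inflated.* The documents give no courtesy rate, and forgetting acts on the same items in the opposite direction.
- *The contraception and pregnancy-planning results will be inflated too.* Women may shade these answers, but they are choices and intentions with no fixed direction to inflate, and the documents do not say which reply would please a clinician.
- *The whole care team can read the answers.* Section 7 does not say so. The overlap arises through staff who hold both roles, and through the open wording on identifiable files.

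**Conclusion.** Courtesy answering may raise two self-reported outcomes: invitation to and attendance at pre-conception counselling, and whether the importance of planning was explained. The visible protocol neither guards against this nor would show it. In-clinic return is the most exposed point.

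The size is unknown. Under an assumed 35% true rate and assumed courtesy rates of 5–20%, the addition is 3.3 to 13 points before forgetting, against a half-width of 9.3 points at n=100. With 20% forgetting as well, the net error runs from −3.8 to +6.0 points, so its sign is not settled. Two opposing unknown errors are still no safeguard. The conclusion rests on the protocol text alone and would weaken if the information sheet already promises separation. It does not call the sample size into question, nor the knowledge items.

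**What to change.** **Section 6**
- Questionnaires completed in clinic are returned in a sealed envelope to a collection box.
- Where the existing team allows, paper and online answers are opened and coded by a research-team member who is not in that woman's direct care. The documents do not show whether such a member is available, so the sponsor should confirm this.
- If this is in place, and the information sheet does not already say so, the invitation and information sheet tell the woman that her treating clinicians will not see her individual answers. The promise should not be made unless the handling supports it.

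**Section 7**
- State that identifiable questionnaires are not open to the woman's own treating clinicians, in place of the present general wording.
- Record the return route (online, post, in clinic) and report the counselling and explanation outcomes by route as a descriptive check. It should not be tested or read as a measure of courtesy bias, because women are not allocated to routes at random and the groups will be small. If 100 returns split evenly, with about 33 per route, the half-width at 35% is 1.96 × √(0.35 × 0.65/33) = 16.3 points.

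**Cost.** Envelopes and a box, a sentence for participants, a task allocation, and treating clinicians not seeing individual answers. The sample size and outcomes do not change. The handling changes must be made before data collection.

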# 7. STATISTICS AND DATA ANALYSIS

Approximately 100 potential participants will be identified from the list of persons who attend the Imperial College Healthcare NHS Trust diabetes clinics. This is based on the known total number of people who attend these clinics (approximately 2000), assuming that 50% will be women and 50% of these will be of reproductive age. All potential participants will be sent the study pack. A response rate of 10-20% is assumed following previous questionnaire studies undertaken at Imperial College of patient populations.

This study contains both descriptive and quantifiable data. The quantitative outcomes may be either ordinal or categorical, and proportions tests, including Chi squared tests, t-tests and ANOVAs will be used to determine differences between these outcomes.

The descriptive data will be tabulated and presented as such without statistical analysis.

All personal details will be sent via encrypted email (nhs.net).

Record linking participant information to study ID will be stored securely on an Imperial College NHS trust Computer. All study data will be stored in a pseudonymised format in an encrypted database on an Imperial College NHS trust computer.

Direct quotations may be published in anonymous fashion. Care will be taken to ensure no other incidental details (such as ethnicity or age) will be associated with the quotation, in order to ensure anonymity. The NHS Code of Confidentiality will be followed at all times. All data is to be stored in a pseudonymised form by using study codes for de-identification of participants. Examples of such a code includes: CAPRE-DM 0001 (assigned in order of enrolment). Identifiable Personal data will be kept in files in a locked office within Imperial College Healthcare NHS Trust, accessible only by the research/clinical team. Pseudonymised data will be stored in a password encrypted spreadsheet on ICHT computers, accessible only by the research team.

Data and all appropriate documentation will be pseudonymised and stored for a minimum of 10 years after the completion of the study in line with Imperial College policy.

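### Section 7 gives about 100 potential participants, but its own inputs give about 500, and n=100 is then reached only at the top of the assumed 10–20% response rate

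*Combined protocol and SAP*

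**What the plan says.** Section 7 (Statistics and Data Analysis) holds the whole justification for the study size. It opens with "Approximately 100 potential participants will be identified from the list of persons who attend the Imperial College Healthcare NHS Trust diabetes clinics". The next sentence bases that number on a known clinic total of approximately 2000, "assuming that 50% will be women and 50% of these will be of reproductive age". It continues "All potential participants will be sent the study pack", and then "A response rate of 10-20% is assumed following previous questionnaire studies undertaken at Imperial College of patient populations".

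Section 6 (Assessment and Follow-up) describes the same process: "All eligible participants will be identified by the clinical care team", working from the database of everyone attending the clinics. They are then contacted by email, by post or in clinic.

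The size of the study is given in two other places: "POPULATION n=100" in the Study Summary and "n=100 participants total" in Section 3 (Study Design). Neither place gives an expected range of respondents, and neither ties the figure to a response rate.

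**The concern.** The number of potential participants does not follow from the inputs said to produce it. Nor can three stated figures hold together: 100 women identified and invited, a 10–20% response, and 100 participants.

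This paragraph is the only basis given for the study size. As written, a reader cannot tell whether 100 is the number invited or the number expected to take part. Staff cannot tell whether to prepare about 100 or about 500 invitations, and any response rate reported later lacks a clear planned denominator. If 100 is the expected number of respondents, it depends on the most favourable end of the plan's own response range, and the plan does not disclose this.

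**Working it through.** **Inputs (all from Section 7 unless noted)**

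- Clinic attendees: about 2000
- Proportion women: 50%
- Proportion of those women of reproductive age: 50%
- Fraction of the pool sent the pack: all
- Response rate: 10–20%
- Stated pool: about 100
- Stated participants: 100 (Study Summary; Section 3)

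**Step 1. Try to reproduce the stated pool.**
Pool = attendees × proportion women × proportion of reproductive age = 2000 × 0.50 × 0.50 = **500**. The stated 100 is not reproduced; the ratio is 500 / 100 = 5. The inputs are approximate, but rounding cannot close this gap. A pool of 100 is 100 / 2000 = 5% of attendees, against the 0.50 × 0.50 = 25% assumed. With half the attendees women, only 100 / 1000 = 10% of them could be of reproductive age.

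**Step 2. Take the stated pool literally.**
Returns = 100 × 0.10 to 100 × 0.20 = **10 to 20**, against n=100.

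**Step 3. Use the pool that the inputs give.**

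| Response rate | Expected returns from 500 | Invitations needed for 100 returns |
|---|---|---|
| 10% | 500 × 0.10 = 50 | 100 / 0.10 = 1000 |
| 15% | 500 × 0.15 = 75 | 100 / 0.15 ≈ 667 |
| 20% | 500 × 0.20 = 100 | 100 / 0.20 = 500 |

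Within the assumed range, 100 appears only as the number of respondents at 20%.

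**Step 4. How likely are 100 returns?**
Let X be the number of returns from 500 invitations, binomial with response probability p (independent responses and a fixed pool of 500 assumed). P(X ≥ 100) is 0.518 at p = 0.20, 0.0015 at p = 0.15 and about 2 × 10⁻¹¹ at p = 0.10. This illustrates how far n=100 depends on the top of the range. It is not a test the plan has to pass.

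**Step 5. What the range means for precision.**
The approximate 95% half-width for a proportion of 50% is 1.96 × √(0.25 / n): 13.9 percentage points at n=50, 11.3 at n=75 and 9.8 at n=100.

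**The case against.** The strongest reply is that this is a slip of one word. The 10–20% response rate stands in the same paragraph and 500 × 20% is exactly 100, so the intended derivation can be recovered. The study is a non-interventional questionnaire that approaches every eligible woman, so correcting the number changes no procedure or analysis. That is fair about the consequences. It does not rescue the sentence: the pack goes to all potential participants, so the response rate acts on the pool and cannot reduce the pool to 100.

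A second reply is that n=100 might mean women approached. Section 6 does sometimes use the word participants for women not yet contacted. But Section 3 sets n=100 beside a time of one hour per participant, and Section 6 makes clear that this hour is for completing the questionnaire. In any case, the gap between 100 and 500 would remain.

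A third reply is that exclusions or approach in clinic change the numbers. The exclusion criteria in Section 4.2 could shrink the pool, but Section 7 applies no such factor. A smaller pool would need a response above 20% to reach 100; a pool of 400, for illustration, would need 100 / 400 = 25%. Approach in clinic might raise response, but no separate rate is given.

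Two criticisms of the supporting figures stand. The plan sets no minimum number, so falling short of 100 breaches nothing in it. The half-widths also assume sampling from a large population: with a finite-population correction for a pool of 500, √((500 − n) / 499), they fall to about 13.2 points at n=50 and 8.8 at n=100. Neither version covers non-response bias, which matters when 80–90% do not reply.

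**Conclusion.** The concern holds. The stated pool is wrong on the plan's own inputs by a factor of five (100 against 500), and no other section corrects it. On the corrected pool, 50–100 returns are expected, so n=100 sits at the upper end of the range.

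The arithmetic rests only on figures in Section 7. Two further points are inference: that the expected returns were written in place of the pool size, and that n=100 counts completed questionnaires. The second is well supported by Section 3. The documents do not quantify losses to the exclusions.

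This should be fixed as a wrong and ambiguous figure in the sole statement of study size. With no power or precision target in the plan, it is not evidence that the study is too small.

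**What to change.** Confirm the pool size from the clinic list, then:

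1. In Section 7, state the number invited and the number expected to respond separately. For example: *About 500 women (2000 × 50% × 50%) are expected to form the pool, and all will be invited; at a response rate of 10–20%, 50 to 100 completed questionnaires are expected.*
2. In the Study Summary and Section 3, replace the bare n=100 with an expected 50–100, noting that 100 is the upper end of the assumed response. If the sponsor means 100 as a target or a maximum, say so instead and give the reason.
3. Say whether the 500 and the 10–20% already allow for women excluded under Section 4.2, and whether the rate applies to all three contact routes.
4. Optionally, give the expected precision: roughly ±14 points at n=50 and ±10 at n=100 for a proportion of 50%, with a note that this leaves out non-response bias.

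The cost is wording plus one check of the list. The stated expected size becomes less favourable; no extra enrolment or change of design is needed.
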